22. DATA ANALYSIS PLANS

22.1 PRIMARY ENDPOINT

Overall response rate (ORR): The overall response rate will be estimated by the number of patients that attain a response (defined above per cohort) by 6 cycles of combination therapy divided by the total number of treated eligible patients. A two-sided 95% confidence interval for the true overall response rate will be calculated according the exact binomial method.

22.2 SECONDARY ENDPOINTS

To additionally assess the efficacy of the combination of ruxolitinib with enasidenib in patients with accelerated or blast-phase disease after 6 cycles of combined therapy using complete (CBR) or partial blast response (PBR). CBR and PBR will be defined according to Appendix A. This will be calculated similarly to the primary endpoint for the MPN-AP/BP cohort.

To assess the efficacy of the combination of ruxolitinib with enasidenib in patients with PMF, post-PV MF, or post-ET MF in chronic phase and 4-9% blasts as assessed by the modified 2013 International Working Group (IWG) Response Criteria, after 6 months of combined therapy. This will be calculated similarly to the primary endpoint for the MPN-AP/BP cohort.

Adverse events: All eligible patients that have been initiated treatment will be included in the calculation of adverse event rate(s). The maximum grade for each type of adverse event will be tabulated for each patient, and frequency tables will be reviewed to determine patterns. Additionally, the relationship of the adverse event(s) to the study treatment will be taken into consideration. Adverse events will be summarized overall and by cohort.

Overall Survival (OS) will be defined as the time from first treatment with the ruxolitinib/enasidenib combination to death by any cause. Patients will be considered censored at the last known date alive, if death is not documented. OS will be estimated using the Kaplan-Meier method.

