11.4 PATIENT ACCRUAL

MPN-RC

Subjects are considered evaluable as long as they have signed informed consent, are eligible for participation and started study treatment. The maximum sample size in the Phase II (accelerated/blast-phase) is 20 evaluable patients. Allowing for enrollment of up to 2 additional patients to account for ineligibility, cancellation, major treatment violation, or other reasons, this study will enroll a maximum of 22 patients in the Phase II AP/BP cohort. The maximum sample size in the chronic phase MPN is 9 evaluable patients. Allowing for enrollment of up to 1 additional patient, this study will enroll a maximum of 10 patients in the descriptive chronic phase MPN cohort. Therefore, a maximum total of 32 (22 + 10) patients will be enrolled in the trial.

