13.3 SAFETY ENDPOINTS

• The proportion of patients developing treatment-emergent hematological and nonhematological adverse events for the combination of ruxolitinib and enasidenib.

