21. SAMPLE SIZE AND ACCRUAL

The maximum sample size in the Phase II (accelerated/blast-phase) is 20 evaluable patients. Allowing for enrollment of up to 2 additional patients as replacements for unevaluable patients (ineligibility, cancellation, major treatment violation, or other reasons), this study will enroll a maximum of 22 patients in the Phase II AP/BP cohort. The maximum sample size in the chronic phase MPN is 9 evaluable patients. Allowing for enrollment of up to 1 additional patient as replacement for unevaluable patients, this study will enroll a maximum of 10 patients in the descriptive chronic phase MPN cohort. Therefore, a maximum total of 32 (22 + 10) patients will be enrolled in the trial.

The anticipated accrual rate is approximately 2-3 patients per month. Therefore, the accrual period for this study is expected to be 15 months. The primary analysis can begin approximately 21 months after the trial begins, i.e., as soon as the last patient has been observed for 6 cycles.

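### The planned adverse event rate tables count only eligible treated patients, so a patient dosed on study and later found ineligible would be left out of them

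*Combined protocol and SAP*

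**What the plan says.** Section 22.2 (Secondary Endpoints, adverse events) sets two conditions for entering the AE rates, eligibility and start of treatment: "All eligible patients that have been initiated treatment will be included in the calculation of adverse event rate(s". Section 22.1 uses the same set, treated eligible patients, as the response denominator.

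Section 11.4 defines an evaluable patient in matching terms: "Subjects are considered evaluable as long as they have signed informed consent, are eligible for participation and started study treatment". Section 21 provides for patients who fall outside that definition: "Allowing for enrollment of up to 2 additional patients as replacements for unevaluable patients (ineligibility, cancellation, major treatment violation, or other reasons". It allows one further replacement in the chronic-phase cohort and caps enrolment at 32.

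The safety endpoint in Section 13.3 is "The proportion of patients developing treatment-emergent hematological and nonhematological adverse events" and does not mention eligibility. The plan defines no all-treated safety population and describes no separate table or listing for treated patients who prove ineligible.

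Other safety provisions have no eligibility condition: AE recording from consent to 30 days after the last dose (Section 17), 24-hour SAE notification whatever the attribution (Section 17.2), the check on the first six patients accrued or enrolled (Sections 10.1 and 20), and DSMB review (Section 24.1).

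**The concern.** Eligibility is a reasonable condition for a response denominator. It is a poor one for toxicity, because a patient becomes at risk by taking the drugs, whether or not every entry criterion was met.

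Three features of this trial give the point weight.

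- Several entry criteria in Sections 8.1 and 8.2 are safety limits: direct bilirubin, creatinine, transaminases, chronic-phase platelets, recovery from earlier toxicity, LVEF and QTcF. A patient found to have breached one of these is plausibly at higher risk of a severe event, and is also the patient the rule removes.
- The trial is open-label and the plan sets no time limit for ruling a patient ineligible. Records are verified during the study (Sections 24.3 and 26), so a ruling could come after toxicity has been seen.
- Sections 10.1 and 20 state that this is the first use of the combination in this population, and safety is a secondary objective (Section 7.2). The AE tables are what later readers will rely on.

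The rule can also produce an awkward result. A related Grade 3 event in one of the first six patients could count towards suspending the trial and then be missing from the final AE rates.

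**Working it through.** **Inputs.** Section 21 gives 20 evaluable plus up to 2 replacements in the accelerated/blast-phase (AP/BP) cohort, and 9 evaluable plus up to 1 in the chronic-phase cohort. Section 22.2 gives the AE denominator.

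**The plan's own figure.** (20 + 2) + (9 + 1) = 22 + 10 = 32, which reproduces the stated maximum. Evaluable patients number 20 + 9 = 29.

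**How many patients could be omitted.** The low end is 0. The high end assumes that every replacement slot is used for a patient who was dosed and later found ineligible:

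| Set | Omitted / all treated | Share |
|---|---|---|
| AP/BP | 2/22 | 9.1% |
| Chronic phase | 1/10 | 10.0% |
| Overall | 3/32 | 9.4% |

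**Effect on a rate.** Let x of n eligible treated patients have the event, and let j of k omitted patients have it. The plan reports x/n; the all-treated rate is (x + j)/(n + k). The plan understates the rate when j/k exceeds x/n and overstates it when j/k is smaller.

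For illustration take x = 8 and n = 29, which are not figures from the documents. The plan would report 8/29 = 27.6%. With k = 3:

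| Omitted patients with the event (j) | All-treated rate |
|---|---|
| 0 | 8/32 = 25.0% |
| 1 | 9/32 = 28.1% |
| 2 | 10/32 = 31.3% |
| 3 | 11/32 = 34.4% |

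With k = 1 the range narrows to 8/30 = 26.7% (no event) and 9/30 = 30.0% (event). The exact 95% interval for 8/29 is 12.7% to 47.2%, so even the extreme case lies inside sampling error.

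**Uncommon events.** Omission shows most here, again with k = 3:

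- An event in 0/29 (0%, exact 95% CI 0 to 11.9%) would be between 0/32 (0%) and 3/32 (9.4%, CI 2.0% to 25.0%).
- An event in 2/29 (6.9%) would be between 2/32 (6.3%) and 5/32 (15.6%).

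If the three omitted patients had an event independently at rate q, the chance that at least one had it is 1 − (1 − q)³: 14.3% at q = 5%, 27.1% at 10% and 48.8% at 20%.

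**The case against.** The strongest reply is that the affected group may be empty. Section 8.0 bars waivers, requires all criteria to be met for registration by the Central Office, and forbids treatment before registration. Section 14.2.1 says registration will not complete if requirements are unmet, and Section 15 places sponsor review of eligibility before enrolment. A dosed patient who proves ineligible has passed through all of these. The Section 21 slots are a contingency that also covers cancellation, major treatment violation and other reasons. A cancelled patient may never be dosed, and an eligible treated patient with a violation stays in the AE set. This stands: the allowance is not a forecast, and 3 is the ceiling it provides for.

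A reader might infer that such patients vanish from safety oversight altogether. The documents do not support that. The recording, SAE reporting, first-six and DSMB provisions still cover them; only the summarised rates are affected.

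A reader might also infer that the rule is bound to bias AE rates downward. That is not shown. Some criteria, such as IDH2 mutation, blast category and a stable ruxolitinib dose, have no evident link to severe events, and omitting patients without the event raises the reported rate. The documents describe no process of declaring patients ineligible after toxicity; they only leave room for it.

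Finally, the silence of Section 13.3 on eligibility is weak evidence of a contradiction. The primary endpoint in Section 13.1 is also stated without an eligibility condition, which Section 22.1 then adds.

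What survives is the rule itself: Section 22.2 states an eligibility condition, and no other provision returns an exposed patient to the AE rates.

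**Conclusion.** The point holds for the planned AE rate tables and no further. As written, a patient dosed on study and later found ineligible is left out of both numerator and denominator.

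The size is 0 to 3 of 32 patients (0 to 9.4%), probably near the low end given the checks before dosing. The upper figure assumes that both cohorts reach their full evaluable number and that every replacement slot goes to a dosed, ineligible patient. The effect on a rate can go either way. Understatement is plausible and is the main concern, because of the safety-limit criteria and the open timing of an ineligibility ruling, but it is not demonstrated. The primary endpoint, the Simon design and its error rates are untouched. The change is still worth making, because in a trial of this size one to three patients can alter whether an uncommon event appears in the tables at all.

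**What to change.** In Section 22.2, replace the eligible-and-treated condition for AE rates with an exposure-based one, for example:

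> *AE rates, overall and by cohort, include all patients who started protocol treatment (at least one on-study dose of study treatment after registration), regardless of later eligibility findings.*

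Add a sentence on patients who enter already taking ruxolitinib. Section 10 has them continue their current dose, so a patient could take ruxolitinib on study and never take enasidenib, while Section 13.3 frames the endpoint for the combination. The plan should state whether such a patient is counted.

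Keep treated eligible patients as the response denominator in Section 22.1.

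The cost is a short text change. AE data are already collected without regard to eligibility, and sample size, significance level, power and visits do not change. The one downside is that reported AE rates may become slightly less favourable.

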22.3 EXPLORATORY/CORRELATIVE ENDPOINTS

• Patient-reported symptoms and quality of MF-SAFv4.0.

The MF-SAF v4.0 will be scored using published scoring algorithms. Patient-reported symptoms and quality of life (QOL) will be described at each time point using the mean, 95%

in Patients with Accelerated/Blast-phase Myeloproliferative Neoplasm or Chronicphase Myelofibrosis with an IDH2 Mutation

(Myeloproliferative Neoplasms Research Consortium [MPN-RC] 119)

confidence interval, median, and range. Changes from baseline will also be described using the mean, 95% confidence interval, median and range, and assessed using paired t-tests or Wilcoxon signed-rank tests as appropriate. Graphical procedures will include plots of average values over time.

• Biomarkers:

Biomarkers will be described at each time point using the mean, 95% confidence interval, median, and range if continuous, or frequency and relative frequency if binary. Continuous changes from baseline will be described using the mean, 95% confidence interval, median and range, and assessed using paired t-tests or Wilcoxon signed-rank tests as appropriate. Binary changes from baseline will be described using frequencies and relative frequencies and assessed using McNemar's tests as appropriate. Biomarker associations with response (IWG/ELN and/or bone marrow) will be primarily descriptive in nature given the small sample size.

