7.3 EXPLORATORY OBJECTIVES

- To determine the impact of the combination of ruxolitinib with enasidenib in patients with PMF, post-PV MF, or post-ET MF, on patient quality of life as assessed by the Myelofibrosis Symptom Assessment Form (MF-SAFv4.0).
- To evaluate the pharmacodynamics of ruxolitinib and enasidenib when combined in this population.
- To evaluate the effects of combined therapy on gene expression and global methylation status.
- To explore changes in mutant allele burden and clonal architecture of disease.

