13.4 EXPLORATORY ENDPOINTS

- The proportion of patients who achieve improvement quality of life as assessed by the by the Myelofibrosis Symptom Assessment Form (MF-SAFv4.0) with the combination of ruxolitinib and enasidenib
- Assess the pharmacodynamics of ruxolitinib and enasidenib when combined in this population.
- Assess the effects of combined therapy on gene expression and global methylation status.
- Assess changes in mutant allele burden and clonal architecture of disease.

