27. WITHDRAWAL OF SUBJECTS

Treatment with study drugs is to be discontinued when any of the following occurs:

- Lack of any response by 6 cycles of combined enasidenib and ruxolitinib therapy (any effort should be made to provide therapy to the patient in a safe way for at least 3-6 cycles for proper assessment of potential efficacy).
- Adverse event(s) that, in the judgment of the Investigator, may cause severe or permanent harm or which rule out continuation of study drug
- Withdrawal of consent
- Lost to follow up
- Toxicity requiring dose modification/treatment suspension, without recovery to baseline, in a patient with less than a CRi
- Death

MPN-RC

The patient will have an end of study visit at 30 days after discontinuation of the protocol treatment ± 7 days to assess for AEs.

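### The MF-SAF endpoint is a proportion of patients improved, but Section 22.3 never estimates one, and its averages after Cycle 7 Day 1 come from a group selected by response

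*Combined protocol and SAP*

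**What the plan says.** Section 13.4 words the endpoint as "The proportion of patients who achieve improvement quality of life" on the MF-SAF v4.0. The matching objective in Section 7.3 is to determine the impact of the combination, in PMF, post-PV MF and post-ET MF, "on patient quality of life as assessed by the Myelofibrosis Symptom Assessment Form (MF-SAFv4.0"). Neither section gives a threshold, a time point or a denominator.

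Section 22.3 plans the mean with 95% confidence interval, median and range at each time point. The same statistics are planned for change from baseline, which is also "assessed using paired t-tests or Wilcoxon signed-rank tests as appropriate". It adds: "Graphical procedures will include plots of average values over time". It names no analysis set and no rule for missing scores.

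Table 4 schedules the questionnaire at every visit of cycles 1 and 2, on day 1 of each later cycle, at end of treatment and at end of study. Survival follow-up records only vital status and current therapy (Section 11.2).

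Section 3 lets accelerated/blast-phase (AP/BP) patients continue after cycle 6 with CR, CRi, PR or complete blast response (CBR). In chronic phase, response is CR, PR or clinical improvement (CI). Section 27 ends study drug for "Lack of any response by 6 cycles of combined enasidenib and ruxolitinib therapy".

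**The concern.** There are two separate problems.

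First, the stated endpoint and the planned analysis do not meet. A team that follows Section 22.3 to the letter finishes the trial without the quantity that Section 13.4 names. Whatever proportion is then reported will have its cut-off, visit and denominator chosen after the data are seen.

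Second, the continuation rule decides who fills in the later forms. In a single-arm trial no control curve would reveal that a falling average reflects who stayed rather than what changed. Section 29 lists symptom and quality-of-life gains among the hypothesised benefits, so these displays are likely to be read as evidence of benefit.

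**Working it through.** **1. Endpoint against analysis.** No arithmetic is needed. Section 13.4 asks for a proportion. Section 22.3 produces means, medians, ranges, paired tests and plots for MF-SAF. None of these is a proportion, and none needs a definition of improvement.

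**2. Does the selection act on symptoms?** In Appendix B, CR and both routes to PR require disease symptoms to have resolved. CI can be met by a symptom response alone, if there is no progression or worsening cytopenia. In Appendix A, CBR rests on blasts and has no symptom criterion. Selection therefore acts partly on symptoms in both cohorts, but not for AP/BP patients who continue on CBR.

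**3. When does it start?** Response is assessed after six cycles. Table 4 places that assessment in the Cycle 7 column, and Section 15 puts marrow and spleen imaging at C7D1. C7D1 is thus plausibly the visit at which non-response is found, so rule-based selection affects the cycle visits after it. Earlier losses come from death, progression, toxicity or withdrawal.

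**4. How many remain?** The plan has no MF-SAF figure to reproduce. Its response rates come from the Simon design (13 patients, stop at 0 responses; 20 in total, success at 3 or more):

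P(success) = Σ (x = 1 to 13) P(X₁ = x) · P(X₂ ≥ 3 − x), with X₁ ~ Bin(13, p) and X₂ ~ Bin(7, p)

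This gives 0.074 at 5% and 0.903 at 25%, against 0.07 and 0.90 in Table 6, so the design reproduces. Expected responders at 25% are 20 × 0.25 = 5 in AP/BP and 9 × 0.25 = 2.25 in chronic phase; at 5% in AP/BP, 20 × 0.05 = 1. These counts omit CBR, so AP/BP retention may be higher.

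**5. Possible size of the selection effect (assumed model).** Let symptom change have true mean zero and SD 1, with correlation ρ to a latent response score. The fraction q with the best scores is retained, above cut-off c. Then

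mean change in retained patients = −ρ · φ(c)/q.

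For q = 0.25, c = 0.674 and φ(c)/q = 1.271. A simulation (20,000 runs, 20 treated, at least 3 retained) gives the chance that a two-sided 5% paired t-test falsely shows improvement:

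| ρ | Mean shift (SD), q = 0.25 | False improvement, q = 0.25 | Mean shift (SD), q = 0.40 |
|---|---|---|---|
| 0 | 0 | 2.6% | 0 |
| 0.3 | −0.38 | 11% | −0.29 |
| 0.5 | −0.64 | 24% | −0.48 |
| 0.7 | −0.89 | 50% | −0.68 |

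The documents give neither ρ nor q for symptoms. At ρ = 0 there is no bias.

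**6. Effect of the denominator (illustration).** Suppose 5 of 20 patients are still treated and 2 of them have improved. Over patients on treatment this is 2/5 = 40% (exact 95% interval 5% to 85%). Over all treated, with missing counted as not improved, it is 2/20 = 10% (1% to 32%).

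**The case against.** The endpoint is exploratory, with no decision rule or alpha attached, in a trial of at most 29 evaluable patients. That stands and limits what is at stake. Four stronger readings are tempting, and the documents do not support them.

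- A reader might infer that the analysis is confined to patients on treatment. Section 22.3 does not say so, and forms are scheduled at end of treatment and end of study, where non-responders would contribute. The fair criticism is that 22.3 does not say how those scores enter the averages.
- A reader might infer that symptoms are bound to appear to improve, or that C7D1 already contains only responders. The direction depends on an unstated correlation, CBR has no symptom criterion, and selection by rule follows the C7D1 assessment.
- A reader might infer a test at each of the 12 post-baseline cycle visits up to C7D1 (3 in cycle 1, 4 in cycle 2, 4 in cycles 3 to 6, and C7D1). Section 22.3 attaches the time points to the descriptive summaries and names no visit for the tests.
- A reader might extend the point to biomarkers. Section 22.3 plans no plots of average biomarker values, and sampling follows its own schedule (Table 5), so the point is not carried over.

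Paired tests also use each patient's own baseline. They therefore avoid the shift in baseline mix that can move a raw average with no patient changing, but they do not remove selection on change itself.

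None of this supplies the missing proportion.

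**Conclusion.** The mismatch between Sections 13.4 and 22.3 is established from the text alone. The selection after C7D1 is also established, provided that Sections 3 and 27 govern continuation. Section 14.0 lists reasons to stop cycles without naming non-response, and these passages must be reconciled. That later cycle-visit averages will look better than the treated population is likely but not certain. The size, 0 to −0.89 SD at 25% retention, rests entirely on the assumed correlation and retention. The impact is limited because the endpoint is exploratory. The correction is still worth making: it is cheap, and it follows the trial's own convention for the primary endpoint.

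**What to change.** In Section 22.3:

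1. Estimate the Section 13.4 proportion at C7D1, by cohort. Define improvement as at least a 50% fall in MF-SAF v4.0 total score, and state that the threshold is borrowed from the Appendix B criterion, which is written for the MPN-SAF total symptom score. Use all treated eligible patients with a baseline score as the denominator, count missing scores and deaths as not improved, and give an exact 95% interval. This matches Sections 20.1 and 22.1, where evaluable patients who do not meet response count as non-responders and the interval is exact.
2. Limit tests of change from baseline to C7D1.
3. Show n at each visit. Present cycle visits after C7D1 descriptively, labelled 'patients still on treatment', alongside the same patients' baseline. Report end-of-treatment and end-of-study scores separately.

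The cost is analysis text and modest programming. The displayed improvement is likely to be smaller, and the proportion will be conservative because missing scores count as not improved.

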23. STUDY MANAGEMENT

23.1 CONFLICT OF INTEREST

Any research personnel who has a conflict of interest with this study (patent ownership, intellectual property, royalties, or financial gain greater than the minimum allowable by their institution, etc.) must declare their conflict of interest to the appropriate institutional review bodies. Local institutional conflict of interest policies will be followed for all research personnel associated with the research project.

